8.3.4. Analysis of Pharmacokinetics

Analysis Set: PK

8.3.4.1. Pharmacokinetic Analysis of MK-3475 and Axitinib

Standard PK parameters for axitinib (C_{max} , T_{max} , $AUC_{0\text{-last}}$, $AUC_{0\text{-12}}$, $AUC_{0\text{-24}}$, CL/F , Vz/F , and plasma elimination half life $t_{1/2}$) will be estimated using non-compartmental methods. For MK-3475, pharmacokinetics will be evaluated at Merck using population pharmacokinetic modeling and results will be shared with pfizer.

Presentation of pharmacokinetic data will include:

- Descriptive statistics (n, mean, SD, %CV, median, minimum, maximum) of plasma concentrations for axitinib will be presented in tabular form by treatment cohort, dose level, cycle, day and nominal time. Additionally similar descriptive statistics will also be generated for dose-normalized axitinib pharmacokinetic parameters
- Linear-linear and log-linear plots of mean and median plasma concentrations by nominal time for axitinib will be presented for PK sampling days by treatment cohort, cycle, and study day. Similar plots will be presented for axitinib for each individual patient concentrations. Only patients who have matched pairs of PK collections available on both planned treatments (when administered alone and in combination with MK-3475) will be included in the axitinib plasma concentration descriptive summary and median concentration profiles. Patients who have undergone intra-patient dose reduction or escalation will be excluded from the median plasma concentration-time plots.
- Pharmacokinetic parameters for axitinib will be listed and summarized by treatment cohort/dose level, cycle and study day using descriptive statistics (n, mean, SD, %CV, median, minimum, maximum, geometric mean and its associated %CV, and 95% confidence interval). For T_{max} , the range (min, max) will be also be provided. Only patients who have a matched pair of estimated axitinib PK parameters available on both planned treatments (when administered alone and in combination) will be included in the axitinib PK parameter summary tables. PK parameters with zero values will be excluded from the calculation of geometric means and its associated %CV. If an intra patient dose escalation or reduction occurs, dose-dependent PK parameters (AUC and C_{max}) for that patient may be dose-normalized when it is known that the drug exhibits linear PK within the dose range and other PK parameters will be reported as estimated; or may only be included in descriptive statistics and summary plots up to the time of the dose change. In addition, dose-normalized axitinib C_{max} and AUC parameters will be summarized (as described above) using data pooled across cohorts in which different axitinib doses were administered.
- Box plots for AUC and C_{max} for axitinib (during treatments when given alone and in combination) will be generated. Individual data points, the geometric mean and the median of the parameter in each treatment will be overlaid on the box plots. If a cohort has limited evaluable PK data (n<4), matchstick plots showing changes in AUC and C_{max} for each drug (during treatments when given alone and in combination) in individual patients will then be generated. The geometric mean of the parameter in each treatment will be overlaid in the plots. In addition, box plots

for dose-normalized axitinib C_{max} and AUC parameters will be created using data pooled across cohorts in which different axitinib doses were administered.

- Trough concentrations for MK-3475, if available, will be plotted for each treatment cohort using a box-whisker plot by cycle and day within cycle in order to assess the attainment of steady-state.

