- The dose-finding component of the trial is completed when 10 DLT-evaluable patients have been treated at the highest dose associated with DLT rate <0.33. It is estimated that approximately 20 DLT-evaluable patients will need to be enrolled to reach 10 DLT-evaluable patients at the estimated MTD.
- The proposed doses, schedule, and PK timepoints may be reconsidered and amended during the study based on the emerging safety and pharmacokinetic data.
- The RP2D will be confirmed in the Dose Expansion Phase, taking into account the MTD determination from the Dose Finding Phase, and other factors related to safety, efficacy, and PK/PD involving all available data from test cohorts.

No intrapatient dose escalation will be permitted in the Dose Finding Phase.

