## **9.5. Analysis of Other Endpoints**

### **9.5.1. Analysis of Pharmacokinetics**

#### **9.5.1.1. Pharmacokinetic Analysis of MK-3475 and Axitinib**

All patients who complete at least one day of PK blood sampling will be included in the PK analyses. Standard plasma PK parameters for axitinib will be estimated using non-compartmental analysis. For axitinib, standard PK parameters will include  $C_{max}$ ,  $T_{max}$ ,  $AUC_{0-12}$ , oral plasma clearance (CL/F), and apparent volume of distribution ( $V_z/F$ ). Descriptive statistics for the PK parameters for axitinib will be provided by dose, cycle and day of assessment in tabular form. For MK-3475, pharmacokinetics will be evaluated using population pharmacokinetic modeling.

All plasma/serum concentrations will be summarized descriptively (n, mean, SD, CV, median, minimum, maximum, geometric mean, its associated CV, and 95% confidence interval) by dose, cycle, day and nominal time. Individual patient and median profiles of the concentration-time data will be plotted by dose, cycle and day (single dose and steady-state) using nominal times. Median profiles will be presented on both linear-linear and log-linear scales.

Trough concentrations for MK-3475 will be plotted for each dose using a box-whisker plot by cycle and day in order to assess the attainment of steady-state.

In addition, Non-linear Mixed Effects Modeling (NONMEM) approaches will be explored to further describe the pharmacokinetic profile and assess potential drug interaction for MK-3475.

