5.4. PK Analysis Set

The PK concentration population is defined as all treated patients who have at least 1 concentration of either of the study drugs.

The PK parameter analysis population is defined as all treated patients who have at least 1 of the PK parameters of interest of any of the study drugs.

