For PK analysis, patients will be required to have at least one quantifiable concentration of each drug to be included in the concentration summary. For evaluation of changes in PK of axitinib when administered alone vs in combination, only patients with matching pair of PK assessments under both conditions will be included in the PK summary. Patients who have been treated with axitinib for whom drug plasma concentrations (from both PK visits, when administered alone and in combination) are available will be included in average concentration summary.

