8.3.4.2. Effect of MK-3475 on Axitinib Pharmacokinetics

The effect of repeated MK-3475 dosing on steady-state axitinib PK will be evaluated using AUC_{0-12} (or AUC_{0-last} , if AUC_{0-12} is not estimable) of axitinib on Lead-in Day 7 and Cycle 7 Day 1, respectively, as the primary PK parameter. Ninety-percent confidence interval for the ratio of geometric means of AUC_{0-12} and C_{max} (axitinib in presence of MK-3475/axitinib alone) will be computed to assess the magnitude of the effect.

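### SAP 8.3.4.1 tabulates Lead-in Day 7 axitinib exposure only in patients who also give a Cycle 7 Day 1 profile, which selects on later outcome and conflicts with protocol 9.5.1.1 and the SAP 5.4 PK sets

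*SAP*

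**What the plan says.** SAP 8.3.4.1 states the matching condition twice. For concentrations, "Only patients who have matched pairs of PK collections available on both planned treatments" are to be "included in the axitinib plasma concentration descriptive summary and median concentration profiles". For parameters, "Only patients who have a matched pair of estimated axitinib PK parameters available on both planned treatments" enter the summary tables. The pooled dose-normalised summaries follow the same description by cross-reference.

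SAP 8.3.4.2 shows which visits form the pair. It uses the AUC "of axitinib on Lead-in Day 7 and Cycle 7 Day 1, respectively, as the primary PK parameter". The protocol's PK sampling schedule contains no other axitinib PK visit.

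Three other rules bear on who is included:

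- Protocol 9.5.1.1: "All patients who complete at least one day of PK blood sampling will be included in the PK analyses".
- SAP 5.4, the set named in SAP 8.3.4: the concentration population needs "at least 1 concentration of either of the study drugs", and the parameter population needs at least one parameter. Neither needs a pair.
- SAP 7.3: "patients will be required to have at least one quantifiable concentration of each drug to be included in the concentration summary". The same paragraph ties a matched-pair rule to the comparison of axitinib alone with axitinib in combination.

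**The concern.** The secondary PK objective has two parts: to characterise axitinib PK, and to assess the effect of MK-3475 on it. Only the second needs two profiles per patient. SAP 8.3.4.1 applies the pairing condition to the tables that serve the first part as well.

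Whether a Lead-in Day 7 profile is tabulated then depends on what happens to the patient over the next 18 weeks. Toxicity leading to a stop, progression leading to a stop, withdrawal, or a missed or invalid Cycle 7 visit all remove it. If any of these is related to exposure, the reported geometric mean, CV and confidence interval describe a selected group. Even if none is, valid data are left out of the tables. A programmer also cannot follow protocol 9.5.1.1, SAP 5.4, SAP 7.3 and SAP 8.3.4.1 at once.

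**Working it through.** The plan states no sample size or precision for these tables, so there is no figure of its own to reproduce.

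**1. Timing.** Cycles last 21 days. Cycle 7 Day 1 falls (7 - 1) x 21 = 126 days, or 18 weeks, after Cycle 1 Day 1. Protocol 7.2.1 also asks for at least 3 days of uninterrupted axitinib before each axitinib PK visit.

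**2. Profiles at risk.** All dose-finding patients (about 20 DLT-evaluable, protocol 3.1.1.2) and at least 8 expansion patients have a lead-in: 20 + 8 = 28. The 8 is a floor and the 20 is a planning estimate, so 28 is an approximate minimum on the planned numbers.

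**3. Illustrative loss.** The documents give no rate of missing Cycle 7 profiles. As a rough proxy, take exponential PFS with the protocol's first-line axitinib median of 10.1 months (95% CI 7.2 to 12.1):

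- t = 126 / 30.44 = 4.14 months.
- Retained share = 0.5^(4.14 / 10.1) = 0.753.
- Lost = 28 x 0.247 = 6.9, so about 21 of 28 remain.
- At a median of 7.2 months the share is 0.671 (about 19 remain). At 12.1 months it is 0.789 (about 22 remain).
- With loss simply assumed at 10% or 40%, 2.8 or 11.2 profiles are lost.

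**4. Possible bias in the Day 7 geometric mean.** The documents give neither the between-patient CV of axitinib AUC nor any link between exposure and loss, so both are assumed here. Let AUC be log-normal with sigma = sqrt(ln(1 + CV^2)). Let the log-odds of loss be linear in z, the standardised log AUC, with the intercept set so that average loss is 24.7%. Then:

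retained / all geometric mean = exp(sigma x E[z | retained]).

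Sigma is 0.385, 0.555 and 0.703 for CV 40%, 60% and 80%. E[z | retained] is -0.097, -0.158 and -0.225 when the odds of loss rise 1.5, 2 and 3 fold per SD. The signs reverse when the odds fall by the same factors.

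| CV | Loss rises with exposure (1.5 to 3 fold) | Loss falls with exposure (1.5 to 3 fold) |
|---|---|---|
| 40% | 0.963 to 0.917 | 1.038 to 1.091 |
| 60% | 0.948 to 0.883 | 1.055 to 1.133 |
| 80% | 0.934 to 0.853 | 1.071 to 1.172 |

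If loss is unrelated to exposure, the ratio is 1. The span at this loss rate is about -15% to +17%. It depends on the loss rate: for CV 80% and a threefold change, E[z | retained] is -0.098 or +0.098 at 10% loss (ratio 0.934 or 1.071), and -0.354 or +0.354 at 40% loss (0.779 or 1.283).

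**The case against.** **Pairing is proper for an interaction study.** It is, for the geometric mean ratio in SAP 8.3.4.2 and for displays that compare the two visits. That does not justify it for a stand-alone description of Day 7.

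**The SAP may depart from the protocol.** Protocol section 9 allows this, and only major changes to the primary endpoint or its analysis need an amendment. These are secondary outputs, so the departure is permitted. But permission does not make selection on a later outcome sound, and the SAP never presents the restriction as a departure. One could say that 8.3.4.1 merely takes a subset of the 5.4 set. Even so, the section names one set and tabulates another.

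**The unpaired data are still visible.** This stands. A reader might infer that every axitinib output is restricted. The listings, individual-patient plots, mean plots and box plots carry no stated pairing limit. What is missing is a table of summary statistics in all patients with Day 7 data.

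**The loss is not mainly toxicity, and PFS is a weak proxy.** This also stands. Treatment may continue past progression, some toxicity is handled by interruption or dose reduction, and a patient who stops MK-3475 may stay on axitinib. The SAP does not say whether a Cycle 7 profile in that last case counts as a combination profile. The share of each cause is unknown.

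**Dose selection is not tied to these tables.** A reader might infer that selection of the recommended Phase 2 dose (RP2D) would be misled. Protocol 3.1.1.2 has that decision draw on "PK/PD involving all available data from test cohorts", and nothing confines it to the tables in 8.3.4.1.

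**SAP 7.3 can be read drug by drug.** It can. On the stricter reading it removes only lead-in patients who never received MK-3475, whom the pairing rule already removes. It would, however, still exclude them from the concentration summary once 8.3.4.1 is corrected.

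**Conclusion.** The point holds for the tabulated axitinib concentration and parameter summaries, including the dose-normalised ones, and for the median profiles. They condition Lead-in Day 7 exposure on being on axitinib and sampled at week 18. This is contrary to protocol 9.5.1.1 and inconsistent with the PK sets in SAP 5.4.

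The conflict of wording is certain. The size is illustrative: about 7 of about 28 profiles, with PFS standing in for retention. The documents do not support a claim that reported exposure would be too low. That reading assumes loss rises with exposure, whereas loss through progression at low exposure would push the other way. The bias is unknown in sign and may be nil. The effect falls on a secondary, descriptive result: its reported n, geometric means, CVs and confidence intervals.

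**What to change.** - In SAP 8.3.4.1, summarise and plot concentrations and parameters by visit (Lead-in Day 7, Cycle 7 Day 1) in all patients of the SAP 5.4 PK sets with axitinib data at that visit, and show n per visit.
- Keep the matched-pair condition only for the interaction analysis in SAP 8.3.4.2 and the displays that compare the two visits.
- In SAP 7.3, require a quantifiable concentration of the drug being summarised, in place of each drug.
- Give the number of unpaired patients with reasons, and show Lead-in Day 7 AUC for paired and unpaired patients side by side, so that any selection can be seen.
- State whether a Cycle 7 profile after MK-3475 has been stopped counts as a combination profile.

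The cost is SAP wording and one extra set of tables, with no new patients or samples. The by-visit tables will no longer hold the same patients at both visits. They should carry a note that comparison between visits belongs to the paired analysis.

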8.3.4.2. Effect of MK-3475 on Axitinib Pharmacokinetics

The effect of repeated MK-3475 dosing on steady-state axitinib PK will be evaluated using AUC_{0-12} (or AUC_{0-last} , if AUC_{0-12} is not estimable) of axitinib on Lead-in Day 7 and Cycle 7 Day 1, respectively, as the primary PK parameter. Ninety-percent confidence interval for the ratio of geometric means of AUC_{0-12} and C_{max} (axitinib in presence of MK-3475/axitinib alone) will be computed to assess the magnitude of the effect.

8.3.4.3. Immunogenicity Assessment

Results for the anti-MK-3475 antibody (ADA) assessment will be provided by Merck.

8.3.4.4. Population Pharmacokinetic Analysis or PK/PD Modeling

Mechanism-based or semi-mechanistic sequential pharmacokinetic-pharmacodynamic models may be developed using NONMEM® to explore any relationships between plasma drug concentrations and selected safety, biomarker, and efficacy endpoints.

The results of these analyses, if performed, will be reported separately.

8.3.5. Analysis of Biomarker Endpoints

Translational and pharmacodynamic biomarkers will be summarized using the appropriate biomarker analysis set. Summaries of baseline and ratio to baseline values at post-treatment visits will be provided using N, mean, standard deviation, median, % CV (as appropriate) and minimum/maximum for circulating biomarkers serum and tumor RNA measurements for potential gene signature development. Summary statistics will be provided for baseline values of circulating markers including VEGF-A, VEGFR2, IL8 and T-cell receptors, and archival tumor and baseline *de novo* biospecimens markers such as PD-L1 for all biomarker evaluable patients. Post-baseline values will be summarized for biomarker evaluable patients in the dose expansion cohort, when available.

Correlations of biomarker results with measures of anti-tumor efficacy will be examined for dose escalation and expansion cohorts separately. Summary of level of biomarkers at baseline and/or ratio of values to baseline versus ORR category will be made by timepoint. Summary of PFS and DR will be provided for dose expansion cohort after stratification by a preset cutpoint of biomarker values at baseline and/or ratio of values to baseline by timepoint. Receiver Operating Characteristics (ROC) analysis may be conducted for significant test results ($p < 0.05$) in correlations of PFS and/or ORR with PD-L1 expression level. Receiver Operating Characteristics (ROC) analysis may also be performed if significant test results ($p < 0.05$) in correlations of ORR and/or PFS with tumor RNA measurements are observed.

Graphical display will be provided for level of biomarkers at baseline and/or ratio of values

to baseline at each timepoint. Box and Whisker plots will be produced for level of biomarkers at baseline and/or ratio of values to baseline versus ORR category by timepoint in dose escalation and expansion cohorts separately. Kaplan-Meier plots will be produced for PFS and DR after stratification by $<$ or \geq median levels of biomarkers at baseline and/or ratio of values to baseline at each timepoint in the dose expansion cohort.

All biomarker data will be listed.

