### **9.5.1.5. Statistical Analysis of Biomarker Endpoints**

Biomarkers will be assessed separately for blood and tumor tissue biospecimens. In each case, summaries of baseline levels and changes from baseline will be reported. Summary statistics may include the mean and standard deviation, median, and minimum/maximum levels of biomarker measures or frequency statistics, as appropriate.

Data from biomarker assays will be analyzed using graphical methods and descriptive statistics such as linear regression, t-test, and analysis of variance (ANOVA). The statistical approach may examine correlations of biomarker results with pharmacokinetic parameters and measures of anti-tumor efficacy.

Due to the exploratory nature of the proposed biomarkers, the data analysis will be conducted with the goal of identifying biomarkers with the strongest concordance to clinical outcome, encompassing both safety and efficacy. Candidate biomarkers will be validated in subsequent trials.

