4. HYPOTHESES AND DECISION RULES

4.1. Statistical Hypotheses

The emphasis of the final analyses will be on estimation of key summary statistics rather than hypothesis testing.

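### SAP 8.3.5 summarises biomarker ratios to baseline by arithmetic mean, SD and %CV alongside the median, but with no geometric mean and no interval; the mean column reads high when ratios vary widely

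*SAP*

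**What the plan says.** For circulating markers and tumour RNA, SAP 8.3.5 plans: "Summaries of baseline and ratio to baseline values at post-treatment visits will be provided using N, mean, standard deviation, median". The list then ends, after a percent sign, with "CV (as appropriate) and minimum/maximum for circulating biomarkers serum and tumor RNA measurements for potential gene signature development". The same section adds a graphical display: "Box and Whisker plots will be produced for level of biomarkers at baseline and/or ratio of values to baseline versus ORR category by timepoint". It also plans Kaplan-Meier plots of PFS and duration of response split at the median marker level or ratio, and a full listing of biomarker data. It names no geometric mean, log transformation or confidence interval for the ratios. The general rule for continuous endpoints in SAP 8.2 does not supply one, and SAP 7.4 deals only with missing and duplicate biomarker values.

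Pharmacokinetics are handled differently. For axitinib parameters SAP 8.3.4.1 lists "median, minimum, maximum, geometric mean and its associated %CV, and 95% confidence interval" in addition to the plain mean, so the unqualified word mean in this SAP is the arithmetic one. For axitinib alone against axitinib with MK-3475, SAP 8.3.4.2 plans a "Ninety-percent confidence interval for the ratio of geometric means".

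Protocol 9.5.1.5 says only that "summaries of baseline levels and changes from baseline will be reported". The choice of ratios is the SAP's own, and Protocol section 9 allows the SAP to modify the plan in this way.

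**The concern.** A ratio to baseline is a multiplicative quantity, bounded below by zero and unbounded above. Averaging it arithmetically gives a doubling more weight than a halving. Whenever patients differ, the mean therefore exceeds the typical ratio, and the excess grows with the spread. The mean column shows a rise when rises and falls balance, and makes falls look smaller than they are. Mean ratios are also not comparable between markers, or between response categories, that differ in variability.

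Exploring the pharmacodynamic effect on markers such as VEGF-A, IL-8 and VEGFR2 is a stated secondary objective, and SAP 4.1 says: "The emphasis of the final analyses will be on estimation of key summary statistics rather than hypothesis testing". In a plan that rests on estimation, the pharmacodynamic change has one centre that is predictably too high (the mean) and one that is sound (the median), and neither has a measure of precision.

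**Working it through.** SAP 8.3.5 gives no expected ratio, spread or precision, so there is no figure of the plan's own to reproduce. The inputs are the statistics listed there, an expansion cohort of up to 40 patients (Protocol summary, Sample Size Determination) and an assumed spread.

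**Step 1, two patients.** One ratio is 2.0 and one is 0.5. Arithmetic mean: (2.0 + 0.5)/2 = 1.25. Geometric mean: √(2.0 × 0.5) = 1.00.

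**Step 2, a general form.** Assume log(ratio) is normal with mean log(g) and SD s. The median and the geometric mean of the ratio both equal g. The expected arithmetic mean is g × exp(s²/2). The documents do not give s, so it is varied from 0.2 to 1.0. The last column is the typical ratio at which the mean would read exactly 1, that is 1/exp(s²/2).

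| s | exp(s²/2) | mean when g = 1.00 | mean when g = 0.70 | mean when g = 0.50 | g at which mean = 1 |
|---|---|---|---|---|---|
| 0.2 | 1.020 | 1.02 | 0.71 | 0.51 | 0.98 |
| 0.3 | 1.046 | 1.05 | 0.73 | 0.52 | 0.96 |
| 0.5 | 1.133 | 1.13 | 0.79 | 0.57 | 0.88 |
| 0.8 | 1.377 | 1.38 | 0.96 | 0.69 | 0.73 |
| 1.0 | 1.649 | 1.65 | 1.15 | 0.82 | 0.61 |

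**Step 3, finite samples.** In 20,000 simulated samples of n = 40 with no true change, the arithmetic mean exceeded 1 in 82% (s = 0.3), 93% (s = 0.5) and 98.5% (s = 0.8) of samples. The median exceeded 1 in about 50%. At n = 8 the corresponding figures for the mean were 64%, 71% and 80%, and for the median 51% to 52%. With a true 30% fall and n = 40, both the median and the geometric mean centred on 0.70 at every s from 0.3 to 1.0.

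**Step 4, spread and precision.** At s = 0.8 and g = 1, the SD of the ratio is 1.377 × √(exp(0.64) − 1) = 1.304. Mean minus one SD is then 1.377 − 1.304 = 0.07, so the SD cannot be read as a symmetric spread. A log-scale 95% interval at n = 40 would be exp(±1.96 × 0.8/√40) = exp(±0.248), or 0.78 to 1.28, around a geometric mean ratio of 1. An interval on the raw scale would be 1.377 ± 1.96 × 1.304/√40, or 0.97 to 1.78. The SAP plans neither; the comparison only shows why an added interval should come from the log scale.

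**The case against.** The strongest reply is that the sentence at issue already contains a sound summary. In the model used here the median ratio equals the geometric mean ratio. At s = 0.8 a true 25% fall would give an expected mean of 0.75 × 1.377 = 1.03, but the median in the same table would be about 0.75. The box plots are centred on the median. A log transform would not change who falls on each side of the median split in the Kaplan-Meier plots, and would not change an ROC analysis. All values are listed. The biomarker work is exploratory, and Protocol 9.5.1.5 leaves validation to later trials. The SAP also lists axitinib concentrations without a geometric mean, so it does not use one for every positive quantity.

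Most of this stands, and it limits the point. A reader might infer that the ratios are summarised by mean and SD alone, or that the plan as a whole would report a rise where nothing changed. The documents do not support that, because the median, range, plots and listings sit beside the mean. A reader might also infer that markers would be ranked partly by their variability. No section ranks markers by mean ratio, and Protocol 9.5.1.5 looks for agreement with clinical outcome, not size of mean change. It would also be wrong to quote only the upper end of the assumed spread: at s of 0.3 or less the distortion is about 5% or less.

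The reply does not cover precision. The undistorted statistic has no interval, and the SAP gives no reason for treating a within-patient biomarker ratio differently from the within-patient axitinib ratio in 8.3.4.2.

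**Conclusion.** The point holds as a minor improvement to the analysis plan. In SAP 8.3.5 the arithmetic mean of the ratios is biased upward relative to the typical multiplicative change, its SD and %CV are dominated by the large ratios, and no centre has a confidence interval. With no true change the expected mean ratio runs from 1.02 to 1.65 as s goes from 0.2 to 1.0: negligible to minor up to about 0.3, material from about 0.5. The direction of the bias needs only that ratios vary between patients; its size rests on the lognormal form and on s, both assumed. Post-baseline tumour numbers may fall below 40 because the second biopsy is encouraged, not required, and in a small sample a few large ratios weigh more heavily on the mean and SD. The summaries are descriptive, and no dose decision or primary endpoint depends on them.

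**What to change.** In SAP 8.3.5, for positive-valued markers, report at each post-treatment visit the geometric mean ratio to baseline, its geometric CV, and a paired 95% confidence interval obtained by back-transforming the interval for the mean log-ratio. Let this replace the arithmetic mean and SD, or name it as the headline with those kept as secondary. Keep the median and the minimum and maximum.

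State a convention for values below the assay limit. SAP 7.4 has none for biomarkers. The rule in SAP 7.3, which sets low axitinib concentrations to zero, cannot be borrowed, since zero has no logarithm and a zero baseline gives no ratio. That convention is the one small downside, and a ratio to baseline needs one in any case when the baseline is unquantifiable. Otherwise the cost is SAP wording and a log transform, with no new data.
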